#### **11.2.1.2 Number of scheduled visits with platelet $\geq 50000/\mu\text{L}$**

The variables to be analyzed are as follows:

- Number of visits with a platelet count of  $\geq 50000/\mu\text{L}$  among 6 visits from Week 2 to Week 12
- Number of visits with a platelet count of  $\geq 50000/\mu\text{L}$  among 12 visits from Week 2 to Week 24

The numbers and percentages of subjects will be presented.

#### **11.2.1.3 Duration of platelet response**

Summary statistics will be presented.

#### **11.2.1.4 Summary statistics of platelet count**

The variables to be analyzed are as follows:

- Platelet count
- Change from baseline in platelet count

Summary statistics will be presented. Additionally, medians and quartiles will be presented graphically.

#### **11.2.1.5 Distribution of platelet count**

The variables to be analyzed are as follows:

- Platelet count:  $< 15000$ ,  $15000 \leq < 30000$ ,  $30000 \leq < 50000$ ,  $\geq 50000/\mu\text{L}$
- Change from baseline in platelet count:  $< 20000$ ,  $\geq 20000/\mu\text{L}$

The numbers and percentages of subjects will be presented.

#### **11.2.1.6 Individual plots of platelet count**

Individual plots and a swimmer plot will be presented for the change in platelet count in each subject. The swimmer plot will show the duration of exposure, as well as the number of days until the following events:

- Maintenance start: The start day of platelet response
- Maintenance end: The end day of platelet response
- Continued response: The end day of the evaluation period when the platelet response is ongoing at the end of the evaluation period.

### **11.2.1.7 Summary statistics of quality of life assessment (SF-36)**

Summary statistics will be presented.

### **11.2.2 Evaluation during long-term treatment of R788**

Applicable period: Long-term treatment of R788

#### **11.2.2.1 Achievement rates for platelet count-related endpoints**

The variables to be analyzed are as follows:

- Achievement rate of a platelet count of  $\geq 50000/\mu\text{L}$  at Weeks 12, 24, 36, 48, and 52
- Achievement rate of a platelet count of  $\geq 30000/\mu\text{L}$  and change from the baseline in platelet count of  $\geq 20000/\mu\text{L}$  at Weeks 12, 24, 36, 48, and 52 (for subjects with a baseline platelet count of  $< 15000/\mu\text{L}$ )

Achievement rates and their two-sided 95% CIs will be presented. All subjects who are not assessed as responders due to discontinuation or missing data will be considered as non-responders.

#### **11.2.2.2 Duration of platelet response**

Summary statistics will be presented.

#### **11.2.2.3 Summary statistics of platelet count**

The variables to be analyzed are as follows:

- Platelet count
- Change from baseline in platelet count

Summary statistics will be presented. Additionally, medians and quartiles will be presented graphically.

#### **11.2.2.4 Distribution of platelet count**

The variables to be analyzed are as follows:

- Platelet count:  $< 15000$ ,  $15000 \leq < 30000$ ,  $30000 \leq < 50000$ ,  $\geq 50000/\mu\text{L}$
- Change from baseline in platelet count:  $< 20000$ ,  $\geq 20000/\mu\text{L}$

The numbers and percentages of subjects will be presented.

#### **11.2.2.5 Individual plots of platelet count**

Individual plots and a swimmer plot will be presented for the change in platelet count in each subject. The dates to be displayed in the figures are as described in “[11.2.1.6 Individual plots of platelet count](#).”

#### **11.2.2.6 Summary statistics of quality of life assessment (SF-36)**

Summary statistics will be presented.

### **11.2.3 Evaluation in Period II**

Applicable period: Period II

#### **11.2.3.1 Achievement rate of platelet response in Periods I and II (sustained stable platelet response)**

This analysis includes data from Periods I and II of subjects who received placebo in Period I and transitioned to Period II.

The achievement rate of sustained stable platelet response in each period and their two-sided 95% CIs will be presented. The difference in the achievement rate between Periods I and II and its two-sided 95% CI will be presented. A CI (normal approximation) based on the standard error of the difference in the rate will be calculated. McNemar test will be used to analyze the difference in the achievement rate between Periods I and II.

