In the C788-049 study, the achievement rate of stable response in subjects randomized to placebo in the C788-047 or C788-048 study was compared with the achievement rate of stable response in these patients after the treatment with R788 (predetermined within-subject and between-study comparison). The stable response was met when the platelet count was increased to $\geq 50000/\mu L$ within 12 weeks after the start of treatment and increased platelet count was maintained for the subsequent 12 weeks. A total of 44 subjects who were randomized to the placebo group enrolled to the C788-049 study; one subject was a responder in the C788-048 study and the other 43 were non-responders. One subject met the criteria for stable response during the treatment with placebo in the C788-048 study, while 10 of these 44 subjects (22.7%) met the criteria for stable response in the C788-049 study, indicating a consistent response rate as compared to the subjects treated with R788 in the C788-047 and C788-048 studies.

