3.2 Secondary Objectives

- 1) To evaluate the efficacy of R788 in patients with chronic ITP for the following points:
 - Maintenance of platelet count during long-term treatment with R788
 - Increase in platelet count during Period II for patients who received placebo in Period I
 - Improving of QOL
- 2) To investigate the safety of R788 in patients with chronic ITP
- 3) To investigate the pharmacokinetics of R788 in patients with chronic ITP (Period I).

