14.5.2.3 Evaluation in Period II

The data in Periods I and II from subjects who receive placebo in Period I and transition to Period II will be analyzed as described in 1). The data in Period II from early transition subjects after completing the treatment with R788 in Period I and those who receive placebo in Period I

and transition to Period II will be analyzed by groups, as specified in 2) to 7). The periods from Weeks 24 to 52 and from ET Day 1 to ET Week 28 will be hereinafter expressed as Day 1 to Week 28 of Period II and Day 1 of Period II will be considered as the baseline of Period II.

1) Achievement rate of maintenance of platelet count in Periods I and II

Considering the subjects who achieve a platelet count of $\geq 50000/\mu L$ within 12 weeks after the start of study treatment in Periods I and II and maintain it for 12 weeks as a responder, the achievement rate with two-sided 95% exact confidence interval (Clopper-Pearson) will be presented. The difference in the achievement rate between Periods I and II and its two-sided 95% exact confidence interval will be presented. McNemar test will be used to evaluate the difference in the achievement rate between Periods I and II.

2) Achievement rate of platelet count

The achievement rate with two-sided 95% exact confidence interval (Clopper-Pearson) will be presented for the following endpoints. Any subject not evaluated as a responder will be regarded as a non-responder.

- Achievement rate of platelet count of $\geq 50000/\mu L$ at Weeks 12, 24, and 28 in Period II
- Achievement rate of a platelet count increase at least 20000/μL above baseline and ≥ 30000/μL at Weeks 12, 24, and 28 in Period II (for subjects with a baseline platelet count of < 15000/μL)
- 3) Duration of stable platelet response

Summary statistics will be presented for the duration of stable platelet response from the first achievement of a platelet count of $\geq 50000/\mu L$ after administration of the study drug in Period II.

- 4) Summary statistics will be presented for the measured value of platelet count and change from the baseline.
- 5) Frequency distributions of platelet count will be presented.
- 6) The time course of platelet count in individual subjects will be presented.
- 7) The summary statistics of the QOL evaluation (SF-36) will be presented.

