## 4. General Principles of Statistical Analysis

- Statistical tests will be performed using a two-sided significance level of 5%.
- Summary statistics will include the number of subjects, mean, standard deviation, minimum, median, maximum, and quartiles.
- Unless otherwise specified, data will be summarized for each analysis group, each period, and each analysis visit.
- For confidence intervals (CIs) of proportions, Clopper-Pearson exact two-sided 95% CIs will be presented for each group, and Chan-Zhang exact two-sided 95% CIs will be presented for between-group differences.

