### **6.5.2 Multiplicity among multiple evaluations**

Stable platelet response is set as the primary endpoint and other variables will be used for reference only. Therefore, multiplicity adjustment among multiple variables will not be performed.

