## 16. Changes from the Protocol

### 16.1 Changes in Statistical Analysis Plan Version 1.0

- 1) In “[3 Analysis Group](#),” the “period I data of subjects who discontinued R788 treatment in Period I” were added to the evaluation during long-term treatment of R788.

Reason: The purpose of this analysis was to evaluate the efficacy and safety of R788 from the start to the end of treatment with the product. Therefore, it was considered appropriate to include subjects who discontinued Period I in the analysis.

- 2) In “[3 Analysis Group](#),” evaluation in the entire study period was added.

Reason: To evaluate platelet response throughout the entire period after study entry.

- 3) In “[5.9 Analysis Visits](#),” the baseline for change calculation was defined as Day 1 of Period I for all periods.

Reason: In the protocol, the baseline was defined as Day 1 of each period. However, it was considered appropriate to use the value not affected by study drug administration as the baseline value.

- 4) In “[6.3.1 Timing of analysis](#),” the scope of data to be cutoff was changed, and variables to be analyzed were clarified.

Reason: To include Period II data in the first data cutoff and the non-dosing period data in the second data cutoff. In addition, variables to be analyzed at the time of cutoff were clarified.

- 5) Evaluation of line of therapy-related variables was added to “[9.1 Subject Demographics](#),” and evaluation of achievement rate of platelet-related endpoints was added to “[11.2.6.1 Platelet response rate](#)” and “[11.3 Subgroup Analysis of Efficacy](#).”

Reason: To evaluate the effect of line of therapy on efficacy, as evaluated in the paper of foreign studies.

- 6) In “[7 Definition of Derived Data](#),” the definition of the start day of platelet response was changed to “the first day after the start of study treatment in each period on which a platelet count of  $\geq 50000/\mu\text{L}$  for at least 28 consecutive days without the use of rescue medications was achieved.”

Reason: To evaluate stable maintenance of platelet count.

- 7) In “[11.1 Primary Endpoint](#),” sensitivity analysis of the primary endpoint planned in the protocol was deleted.

Reason: A blind review confirmed that no subject would need imputation of missing

platelet count data for the evaluation of stable platelet response. It was thus decided not to perform sensitivity analysis because no imputation would be performed.

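### The SAP replaces the protocol's exact 95% interval for the placebo-to-R788 within-subject difference with a normal approximation on about 8 pairs, and does not list the change

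*SAP*

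**What the plan says.** The comparison concerns subjects given placebo in Period I who then receive R788 in Period II. Each is classed as a responder or not in each period, so the data are pairs.

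- Protocol 14.5.2.3, item 1: "The difference in the achievement rate between Periods I and II and its two-sided 95% exact confidence interval will be presented".
- SAP 11.2.3.1, for the same difference: "A CI (normal approximation) based on the standard error of the difference in the rate will be calculated". The section also plans a McNemar test and an interval for each period's own rate. It does not give the standard-error formula or say whether McNemar is asymptotic or exact.
- SAP section 4: Clopper-Pearson intervals for single proportions, and "Chan-Zhang exact two-sided 95% CIs will be presented for between-group differences". A within-subject difference between periods is not a between-group difference.
- SAP section "16. Changes from the Protocol" itemises departures for versions 1.0, 2.0 and 3.0. No item refers to 11.2.3.1 or to this interval.
- Protocol 3.2 names the underlying question as a secondary objective: "Increase in platelet count during Period II for patients who received placebo in Period I". SAP 6.5.2 adds that, apart from the primary endpoint, "other variables will be used for reference only".
- Protocol 8.9.1 plans 8 placebo subjects. The number who enter Period II is not given.

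**The concern.** Two things look wrong. First, a prespecified method was changed without being recorded, in a SAP whose list of changes goes down to blood-pressure and ALT/AST categories. Second, the new method relies on a large-sample approximation for about 8 pairs, few of which are likely to be discordant.

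This interval is the error bar for the effect of switching from placebo to R788. The protocol describes the same predetermined within-subject comparison in the overseas extension study, so it is a natural bridge between Japanese and overseas results. An interval of zero width, or one that extends beyond a possible difference, would misstate how much 8 patients can show.

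**Working it through.** **Inputs.** Pairs: n = 8 (Protocol 8.9.1), fewer if some placebo subjects do not transition. Rates (Protocol 1.3.2.2): "One subject met the criteria for stable response during the treatment with placebo in the C788-048 study", that is 1/44, while "10 of these 44 subjects (22.7%) met the criteria for stable response in the C788-049 study". 10/44 = 22.7%, as stated. The documents give no precision or power figure for this comparison.

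**Formulas.** Let b be the number responding only in Period II and c the number responding only in Period I. The estimate is d = (b − c)/n and the interval is d ± 1.96 × SE. Because the SAP does not define SE, two versions were tried:

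- Wald (unrestricted): SE = √[(b + c) − (b − c)²/n] / n
- null (McNemar): SE = √(b + c) / n

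Coverage was found by enumerating every (b, c) under the trinomial distribution.

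**Probabilities.** With the periods independent, P(Period II only) = 10/44 × 43/44 = 0.2221 and P(Period I only) = 1/44 × 34/44 = 0.0176. The true difference is 9/44 = 0.2045. Independence is not essential. The overseas margins allow only two paired tables: the one placebo responder also responded on R788 (9/44 and 0), or did not (10/44 and 1/44).

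**Coverage of the nominal 95% interval**

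| Pairs | Wald, independent | Wald, 9/44 and 0 | Wald, 10/44 and 1/44 | Null SE, independent |
|---|---|---|---|---|
| 6 | 75.5% | 72.8% | 76.2% | 77.8% |
| 8 | 85.1% | 82.8% | 85.6% | 86.6% |
| 12 | 91.9% | 91.4% | 91.8% | 94.6% |

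**Where the shortfall comes from** (8 pairs, Wald, independent). If no pair is discordant, both SE formulas give 0 and the interval is 0 to 0. That has probability (1 − 0.2221 − 0.0176)⁸ = 0.112, or 16.0% and 10.0% under the two paired tables. Of the 15.0 points of non-coverage, 13.4 are intervals wholly below the true difference (11.2 of them the 0-to-0 case) and 1.5 are wholly above it.

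**Individual outcomes at 8 pairs, c = 0**

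| b | Wald | Null SE | McNemar p, asymptotic | McNemar p, exact |
|---|---|---|---|---|
| 0 | 0 to 0 | 0 to 0 | – | 1 |
| 3 | 0.04 to 0.71 | −0.05 to 0.80 | 0.083 | 0.25 |
| 6 | 0.45 to 1.05 | 0.15 to 1.35 | below 0.05 | 0.031 |

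At b = 3 the Wald interval excludes 0 while McNemar does not reject. The chance of such a conflict with asymptotic McNemar, at the overseas rates, is 16% with the Wald SE and 0% with the null SE.

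**Other rates** (8 pairs, Wald). With a Period I-only rate of 2%, coverage is 89%, 94%, 85% and 93% at Period II-only rates of 30%, 35%, 40% and 50%. It is 99% at 5% and 5%. At the primary-endpoint planning rates (2.0% and 17.8%, Protocol 8.9.2; a related but different endpoint) it is 78%.

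**An exact alternative.** An unconditional interval based on the Tango score statistic (two one-sided 2.5% tests, maximised over the nuisance parameter) covers 99.8% at 8 pairs and the overseas rates. It gives −0.37 to 0.37 when no pair is discordant and −0.10 to 0.76 at b = 3.

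**The case against.** The strongest reply accepts the discrepancy and disputes its weight.

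- *The 85% is nearly all one obvious outcome.* Given at least one discordant pair, Wald coverage at 8 pairs is 0.8505/(1 − 0.1117) = 95.7% under independence, and 98.6% and 95.1% for the two paired tables. A 0-to-0 interval is plainly degenerate, and it would sit beside each period's own exact interval (0 of 8 gives 0 to 37%). The arithmetic stands. But the degenerate interval is still what the plan would report, in 10% to 16% of trials at these rates. Nor is it the only cause elsewhere: with rates of 40% and 2%, dropping that outcome raises coverage only to 0.847/(1 − 0.58⁸) = 86%.
- *The figure depends on unstated quantities.* This stands. The number of pairs, the SE formula and the true rates are not fixed, and coverage is near nominal at some rates. At 8 pairs and the overseas rates, however, the null SE does little better, and fewer pairs make both worse.
- *The exact interval has faults too.* This stands. It is conservative and wider, and it can also disagree with the planned test: b = 4 gives −0.05 to 0.84 with asymptotic p = 0.046. Agreement with McNemar is therefore not a reason to prefer it.
- *Little hangs on it.* This also stands. The endpoint is for reference, McNemar and the per-period intervals remain, and individual platelet plots will show every subject.

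**Conclusion.** The concern holds. The switch from exact to normal approximation, and its absence from SAP section 16, are matters of text and need no assumption. The loss of coverage is conditional: about 85% (83% to 86% over the two paired tables) with the Wald SE, 8 pairs and the overseas rates, and 87% with the null SE under independence. With either SE the interval can have zero width or exceed 1.

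The error mainly understates the benefit of R788 and overstates precision; it is unlikely to create a false benefit. The primary conclusion is unaffected. This should be corrected, but it does not threaten the trial's main result.

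**What to change.** Delete the normal-approximation sentence from SAP 11.2.3.1 and restore the protocol's exact 95% interval, naming a method for paired differences, for example the exact unconditional score-based interval used above. If the sponsor prefers to keep the approximation, list and justify the change in SAP section 16 and write out the SE formula. In either case, say whether McNemar is asymptotic or exact.

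The cost is one sentence and a short program; SAP section 14 already allows other software. The price is a wider, conservative interval: mean width 0.85 against 0.53 for Wald at 8 pairs and the overseas rates.

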#### **11.2.3.2 Achievement rates for platelet count-related endpoints**

The variables to be analyzed are as follows:

- Achievement rate of a platelet count of  $\geq 50000/\mu\text{L}$  at Weeks 36, 48, and 52
- Achievement rate of a platelet count of  $\geq 30000/\mu\text{L}$  and change from the baseline in platelet count of  $\geq 20000/\mu\text{L}$  at Weeks 36, 48, and 52 (for subjects with a baseline platelet count of  $< 15000/\mu\text{L}$ )

Achievement rates and their two-sided 95% CIs will be presented. The difference in the achievement rate between groups and its two-sided 95% CI will be presented. All subjects not assessed as responders due to discontinuation or missing data will be considered as non-responders.

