8.3.1 Transition criteria to Period II for subjects who withdraw from Period I

- 1) Subjects who meet any of the following criteria and withdraw from Period I due to "2) Lack of efficacy (inadequate response)" in "5.3.1 Withdrawal criteria (withdrawal in individual subjects)"
 - Subjects with a platelet count of $\geq 15000/\mu L$ on Day 1:
 - a) Platelet count of $< 50000/\mu$ L after Week 12 despite the increased dose to 150 mg *bid* for more than 4 weeks.
 - b) Platelet count of $< 50000/\mu$ L after Week 12 because of the inability to increase the dose to 150 mg *bid* due to possible poor tolerability.
 - Subjects with platelet count of < 15000/μL on Day 1:
 - a) Platelet count increase of $< 20000/\mu$ L from Day 1 after Week 12 despite the increased dose to 150 mg *bid* for more than 4 weeks.
 - b) Platelet count increase of $< 20000/\mu$ L from Day 1 after Week 12 because of

the inability to increase the dose to 150 mg *bid* due to possible poor tolerability.

- 2) Subjects with systolic blood pressure of < 140 mmHg and diastolic blood pressure of < 90 mmHg on ET Day 1 whether or not the subject is receiving antihypertensive treatment
- 3) Subjects without the following laboratory abnormalities on ET Day 1:
 - White blood cell count $< 2000/\mu L$
 - Neutrophil count < 1000/μL
 - Lymphocyte count $< 750/\mu L$
 - Hemoglobin < 10 g/dL
- 4) Subjects without the following laboratory abnormalities on the last laboratory test before ET Day 1
 - ALT or AST $> 1.5 \times ULN$
 - Total bilirubin $> 1.5 \times ULN$
 - eGFR < 30 mL/min
- 5) Subjects who do not have significant infection, an acute infection such as influenza, or inflammatory process on ET Day 1.
- 6) Subjects who have not received blood or blood products within the 2 weeks prior to ET Day 1 (intravenous immunoglobulin or platelet transfusion are allowed if used for rescue therapy).

8.3.2 Rationale for transition criteria to Period II for subjects who withdraw from Period I

- 1) This criterion was set to include subjects who withdraw from Period I due to lack of efficacy.
- 2) to 5) These criteria were set to ensure the safety of subjects.
- This criterion was set to exclude the matters that might affect the efficacy evaluation of R788.

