## 3. Analysis Group

Unless otherwise specified, the analysis will be performed on the following subjects and data. For FAS analysis, “treated subjects” will be handled as “randomized subjects.”

- 1) Evaluation in Period I
  - R788 group: Period I data of subjects who received R788 in Period I
  - Placebo group: Period I data of subjects who received placebo in Period I
- 2) Evaluation during long-term treatment of R788
  - R788 group: The analysis will be performed on the following subjects and data:
    - Period I data of subjects who received R788 in Period I
    - Period II data of subjects who received R788 in Period I, completed treatment with R788 in Period I and transitioned to Period II (subjects on long-term treatment of R788)

3) Evaluation in Period II

- R788-R788 group: Period II data of subjects who received R788 in Period I and early transitioned to Period II after discontinuing Period I
- P-R788 group: Period II data of subjects who received placebo in Period I and transitioned to Period II

4) Evaluation in non-dosing period

- R788 group: Non-dosing period data of subjects who transitioned to the non-dosing period (subjects who transitioned from Period II to Period III without non-dosing period are excluded).

5) Evaluation in Period III

- R788 group: Period III data of subjects who transitioned to Period III

6) Evaluation in R788 treatment period

- R788 group: The analysis will be performed on the following subjects and data:
  - Data from Period I, Period II, and Period III of subjects who received R788 in Period I
  - Data from Period II and Period III of subjects who received placebo in Period I and transitioned to Period II

7) Evaluation in the entire study period

- R788-R788 group: Data from Period I, Period II, non-dosing period, and Period III of subjects who received R788 in Period I
- P-R788 group: Data from Period I, Period II, non-dosing period, and Period III of subjects who received placebo in Period I

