### 3) Evaluation in Period II

The following data will be used as Week 24 to 52 data:

- Data from Week 24 to 52 of subjects who received placebo in Period I, completed Period I, and transitioned to Period II.
- Data from early transition Day 1 to early transition Week 28 of subjects who discontinued Period I and early transitioned to Period II.

**Table 5.9-5** Analysis Visits in Period II

Variables evaluated	Analysis visit
Platelets	Week 24 to 52 (every 4 weeks)
Treatment dose	Week 24 to 52 (every 4 weeks)
QOL assessment (SF-36)	Week 24, Week 52
ITP Bleeding Score	Week 24 to 52 (every 4 weeks), LOV
ECOG Performance Status	Week 24 to 52 (every 4 weeks), LOV
Hematology (excluding platelets)	Week 24 to 52 (every 4 weeks), LOV
Serum chemistry	Week 24 to 52 (every 4 weeks), LOV
Urinalysis	Week 24, Week 28 to 52 (every 12 weeks), LOV
Immunoglobulin test	Week 24, Week 52, LOV
Vital signs	Week 24 to 52 (every 4 weeks), LOV

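### SAP 11.2.3.2 reports a Period II between-group difference with a 95% CI, but post-randomisation selection on outcome forms the groups, so it is not a treatment effect

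*SAP*

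**What the plan says.** SAP 11.2.3.2 covers two single-visit endpoints in Period II, at Weeks 36, 48 and 52. One is a count of at least 50000/µL. The other, for subjects with a baseline below 15000/µL, is a count of at least 30000/µL with a rise of at least 20000/µL. After the per-group rates it adds: "The difference in the achievement rate between groups and its two-sided 95% CI will be presented". SAP section 4 makes this a Chan-Zhang exact interval.

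SAP section 3, item 3, defines the only two groups for this evaluation:

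- R788-R788: "Period II data of subjects who received R788 in Period I and early transitioned to Period II after discontinuing Period I".
- P-R788: "Period II data of subjects who received placebo in Period I and transitioned to Period II".

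R788 subjects who completed Period I are placed in the long-term evaluation instead, which takes "Period II data of subjects who received R788 in Period I, completed treatment with R788 in Period I and transitioned to Period II". Placebo completers do stay in the Period II evaluation: SAP 5.9, item 3, includes "Data from Week 24 to 52 of subjects who received placebo in Period I, completed Period I, and transitioned to Period II".

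Early transition is governed by Protocol 8.3.1. The rationale for its first criterion reads: "This criterion was set to include subjects who withdraw from Period I due to lack of efficacy".

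For the same endpoints, Protocol 14.5.2.3 item 2 plans only per-group rates with Clopper-Pearson intervals. It asks for no between-group difference.

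**The concern.** A difference with an exact interval between columns headed R788-R788 and P-R788 looks like a comparison of the two randomised arms carried into Period II. It is not. One column keeps only the drug's early failures, while the other keeps every placebo subject who went on to their first R788. A gap between them can arise from how the columns were filled. A reader of the clinical study report could take it as evidence about continuing R788 compared with starting it later. What is at stake is the interpretation of one secondary table.

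**Working it through.** **1. Which groups are compared.** SAP 11.2.3.2 names no groups of its own, so those of SAP section 3, item 3, apply: R788-R788 and P-R788. Protocol 14.2 words the first group differently (after completing R788 treatment in Period I, where the SAP says after discontinuing Period I). Both restrict it to early transition subjects, so the point holds under either wording.

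**2. How R788-R788 is selected.** Protocol 8.3.1 requires withdrawal for lack of efficacy plus a platelet criterion after Week 12. Set beside the endpoints of SAP 11.2.3.2:

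| Day 1 count | Early-transition criterion | Endpoint already failed |
|---|---|---|
| ≥ 15000/µL | count < 50000/µL | ≥ 50000/µL |
| < 15000/µL | rise < 20000/µL from Day 1 | rise ≥ 20000/µL with count ≥ 30000/µL; also ≥ 50000/µL, since the count is below 15000 + 20000 = 35000/µL |

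SAP 5.9 uses Period I Day 1 as baseline throughout, so the rise is measured from the same point in both columns of the comparison. SAP 11.1 counts anyone who discontinues for lack of efficacy as a non-responder. R788-R788 therefore contains no Period I stable responder, by definition.

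**3. How P-R788 is selected.** It takes placebo completers and placebo early transitioners. The latter failed on placebo, which says nothing direct about their response to R788. The groups also differ in prior R788 exposure: at least about 12 weeks against none. SAP 6.1 rules out covariate adjustment.

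**4. Where the SAP sets this contrast apart.** The sentence matches the one in SAP 11.2.1.1 for Period I, where the groups are randomised and the contrast is valid. For adverse events, SAP 12.1.1 limits the between-group difference to Period I. SAP section 16 does not list the Period II difference as a change from the protocol.

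**5. Size of the selection effect.** The plan gives no figure for this contrast. Its one design figure is the 89% chance in Protocol 8.9.2 that the R788 point estimate exceeds placebo. It reproduces at 89.3% by exact enumeration (16 vs 8 subjects, 17.8% vs 2.0%, ties not counted), and nothing here depends on it.

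For illustration, let every subject have the same probability m of responding on R788 in either period, with within-subject correlation ρ between the two responses. Let R788-R788 be representative of R788 non-responders, and P-R788 be unselected for response to R788. These are assumptions, not document facts.

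- P(response in both periods) = m² + ρm(1−m).
- P(Period II response given Period I non-response) = [m − m² − ρm(1−m)]/(1−m) = m(1−ρ).
- Expected difference, R788-R788 minus P-R788 = m(1−ρ) − m = −mρ.

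| m | ρ = 0 | ρ = 0.5 | ρ = 0.8 | ρ = 1 |
|---|---|---|---|---|
| 17.8% (assumed R788 rate, Protocol 8.9.2) | 0 | −8.9 | −14.2 | −17.8 |
| 22.7% (10/44 placebo switchers, overseas extension, Protocol 1.3.2.2) | 0 | −11.4 | −18.2 | −22.7 |

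Entries are percentage points. Neither m is a rate for the single-visit endpoints: 17.8% is stable response and 22.7% is sustained response over 12 weeks.

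**6. Precision.** Expected R788 non-responders: 16 × (1 − 0.178) = 13.2. If 50% to 100% of them transition early, R788-R788 has about 7 to 13 subjects, against at most 8 in P-R788. Two invented results, with approximate Chan-Zhang limits on a 0.02 grid:

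- 0/10 vs 2/8: −25 points, 95% CI about −64 to +8.
- 0/13 vs 2/8: −25 points, 95% CI about −64 to +4.

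**The case against.** The strongest reply is that little turns on this output. It has no test attached. SAP 6.5 treats everything except the primary endpoint as reference material. With at most 8 placebo subjects the interval will be very wide, and both examples above include zero. The protocol itself has these two groups analysed side by side, so a reader can subtract the rates whether or not the SAP does. Protocol section 14 leaves detailed methods to the SAP and allows further analyses, so adding a contrast is not in itself a fault.

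Most of this stands, and it limits the weight of the point. It does not make the contrast meaningful. The reference-only status in SAP 6.5 answers multiplicity, not selection. A formal interval gives the gap a standing that two adjacent rates do not have. No passage tells the reader how the groups came about.

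Two stronger readings are tempting, and the documents do not support them. A reader might set an early-transition rate of 0% to 5% against 22.7% and infer a bias of −18 to −23 points from selection alone. The documents give no Period II rate for R788 early transitioners, and failure judged after Week 12 does not prove that a later single count cannot reach 50000/µL. In the illustration above, that range needs ρ of about 0.8 or more. A reader might also infer that the trial's efficacy conclusion is compromised. It is not: the primary analysis uses Period I data and the randomised groups.

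**Conclusion.** The point holds at low severity. By the group definitions alone, the Period II difference in SAP 11.2.3.2 compares early failures on R788 with subjects who had not yet taken it, so it does not estimate a treatment effect. The direction, unfavourable to R788-R788, follows if response is positively correlated within subject and the drug otherwise acts alike in both groups. The size is not fixed by the documents. It runs from 0 to about −23 points for ρ from 0 to 1 at an assumed common rate of 22.7%, which is borrowed from a different endpoint. The primary conclusion is unaffected.

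**What to change.** Delete the between-group difference and its interval from SAP 11.2.3.2. Present each group's rate with its Clopper-Pearson interval, as Protocol 14.5.2.3 item 2 plans. This removes one sentence and one output and needs no new data.

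If the sponsor prefers to keep the difference, label it in the table as a non-randomised contrast between groups formed by post-randomisation selection, state that it is not a treatment effect, and list the addition with its reason in SAP section 16.

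Do not replace it with a comparison of P-R788 in Period II against the R788 arm in Period I. That contrast is confounded too. It sets placebo subjects who reached Period II against all R788 subjects, and open-label against double-blind treatment (Protocol 8.1). The starting regimens can differ (Protocol 8.6.1). Tapering of allowed ITP therapy at a stable count of at least 50000/µL is permitted in Period II but not in Period I (Protocol 8.7.7).
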